More effective and efficient gingival displacement procedure can lead to clinically improved fixed restorations, less patient chair time, and less patient discomfort.

Materials and Methods: One hundred (100) patients will be recruited from the University of North Carolina (UNC) School of Dentistry (SOD). A stratified block randomization will be used to randomize patient to impression technique: Aquasil Ultra Cordless, Dentsply International using Aquasil Ultra Polyvinyl siloxane (PVS) impression material versus Dentsply International, gingival displacement cord (Ultrapak, Ultradent Products International) hydrated with aluminum chloride hexahydrate (Hemodent, Premier Dental Products Company). Stratification will be based on the clinic where treatment is provided (Dental Faculty Practice, Graduate Operative Dentistry, Graduate Prosthodontic Clinic), A block size of 4 within each stratum will be used to maintain a balanced allocation to impression group. Patient inclusion criteria include: 1) requires indirect restoration 2) probing depths 4mm or less. 3) No bleeding on probing. 4) finish line 0-1mm sub-gingival.

Specific Aims

The intent of this exploratory study is to compare two methods (cordless vs corded gingival displacement) currently used in clinical practice to displace sulcular tissues to facilitate an acceptable dental impression that accurately captures the prepared cervical finish line for the fabrication of indirect fixed prosthodontic restorations. The primary aims are to compare the two methods with respect to 1) the accuracy of the impression with respect to capturing the prepared cervical finish line for the fabrication of the indirect fixed prosthodontic restoration as assessed by two expert clinicians 2) the time required to prepare the impression and 3) the discomfort of the procedure as reported by the patient. Secondary aims are to estimate the effect of clinician experience (resident level vs faculty) and jaw of restoration placement (maxillary vs mandibular) on the outcomes of accuracy, time, and discomfort.

Significance

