A total of one hundred participants will be recruited from the University of North Carolina (UNC) School of Dentistry (SOD) Graduate Prosthodontics clinic, Graduate Operative clinic, and the Dental Faculty Practice. A stratified block randomization will be used to randomize patient to impression technique: Aquasil Ultra Cordless, Dentsply International using Aquasil Ultra Polyvinyl siloxane (PVS) impression material versus Dentsply International, gingival displacement cord (Ultrapak, Ultradent Products International) hydrated with aluminum chloride hexahydrate (Hemodent, Premier Dental Products Company). Stratification will be based on the clinic where treatment is provided (Dental Faculty Practice, Graduate Operative Dentistry, Graduate Prosthodontic Clinic). A block size of 4 within each stratum will be used to maintain a balanced allocation to impression group. The randomization schedule will be prepared by [name]. Randomization allocations will be placed in sequentially numbered envelopes for ease of use by clinicians within the three clinics.

The treating clinician will open the allocation envelope after the tooth preparation is completed. This is to limit the potential bias of the clinician altering the tooth preparation design in anticipation of a known gingival displacement technique. Although the patient may require restorations on multiple teeth, only one tooth, the most posterior, will be included in the evaluation. The clinician will be instructed to

complete the impression for that tooth before proceeding to other teeth. The patient will be informed that participation, if multiple teeth are treatment planned, may increase the appointment time.

The gingival displacement procedures and impression procedures are described here:

Traditional Corded Impression Procedure:

- 1) The prepared tooth is washed and dried, and assure hemostasis.

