- 4) An impression tray that has been filled with the heavy body consistency impression material is then placed over the arch of teeth, and gently pressed into place to ensure the teeth are completely covered with a uniform thickness of impression material. As the different impression material consistencies set, they fuse together into a single unit.
- 5) When removed from the mouth, the impression should contain a negative copy of both the prepared tooth and the teeth of that jaw.

The clinician will record the impression technique, type of impression material used; whether tray adhesive was used; the tray material; the type of tray used; the number of units requested; the time required to obtain the first impression (start and end of impression taking is defined above for each procedure), and the total number of impressions produced until an adequate impression was made. Also recorded will be the clinic and resident year if placed in a graduate clinic and the subject's age and sex. Unique id numbers not related to clinical record will be used.

The impressions will be photographed, digitally scanned, saved in black and white, and then collectively evaluated at a later time based on a criteria evaluation form by two calibrated evaluators. The evaluators (also referred to as expert examiner) will assess each impression for errors in the finish line; in the tray/material; and errors with gingival displacement/hemostasis as primary outcomes. The number of errors can range from 0 to 13.

Patient discomfort will be assessed using the FACES visual picture pain scale rated from 1-10 based on the following question posed at 4 points during treatment; "How much discomfort are you experiencing at this point in treatment?" This question will be asked at the beginning of the treatment appointment, immediately before the impression procedure is initiated, immediately after the impression procedure is completed, and again at the completion of the treatment appointment. Each question will be rated on a scale of 1 to 10. The total score indicated by the sum of the 4 questions will be analyzed.

Patient consent will be obtained prior to treatment and the impression. This may occur at a prior treatment planning visit or at the treatment visit.

Inclusion Criteria:

- Patients must be adult males or females 18 years of age or older.
- Patients must be able and willing to follow study procedures and instructions.

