- Patients must have read, understood and signed an informed consent form.
- Patients must be in good general health, (based on a review of the medical history, blood pressure and heart rate).
- Patients must have no health-related contra-indications to dental treatment.
- Patient must require at least one indirect restorations (crowns).
- Probing pocket depths around the treatment tooth/teeth must be 4mm or less.
- There must be no bleeding on probing around the treatment tooth/teeth.
- The prepared finish line must be between 0 to 1mm sub-gingival (inclusive).

Exclusion Criteria:

- Individuals who have a chronic disease with oral manifestations.
- Individuals who exhibit gross oral pathology.
- Smokers
- Uncontrolled Diabetics (per review of medical history)
- Probing pocket depths around treatment tooth/teeth of greater than 4mm.
- Bleeding on probing around treatment tooth.teeth.
- The prepared finsh line is greater than 1mm sub-gingival.

The inclusion/exclusion criteria limit generalizability of the findings to patients without confounding periodontal or medical issues. However, the sample size of this study is not sufficient to extend to a consideration of the effect of these confounders on the comparison of the two impression techniques.

The proposed research study requires a total of 100 participants. Patients will be recruited from and will be treated in the Dental Faculty Practice, the Graduate Operative Clinic, and the Graduate Prosthodontic Clinic. The patient may seek other dental treatments in the above mentioned clinics or in other clinics in the School of Dentistry.

Study clinicians will be trained and calibrated on both the cordless and the corded gingival displacement procedures and impression procedures in a practice session. Clinical instruction protocols will be printed on laminated forms for all study clinicians to follow, for both the cordless and the corded procedures. These clinical protocol forms will be in the clinicians operatory during actual study treatment, and this protocol must be followed for the impression to be included in the study. The clinical instruction protocol is listed in Appendix A.

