In addition to a signed Consent form, the study subject will be asked to complete the standard adult medical and dental health history questionnaire provided by the UNC SOD (Appendix 1) and will be provided with the UNC Chapel Hill Notice of Privacy Practices and the Consent for Purposes of Treatment, Payment and Health Care Operations (Appendix 2). Other than the research consent, these are standard practices followed by UNC SOD for all patients. The study is mandated to adhere to these protocols prior to treating a patient at the UNC SOD. After consent has been obtained, an oral examination will be performed by the treating dentist to confirm the patient meets inclusion criteria. The patient will be dropped from the study if inclusion/exclusion criteria are not met. The treating clinician will record the criteria that resulted in the patient being dropped (See Appendix B). If the inclusion criteria are not met, a clinically appropriate impression method will be performed at the clinician's judgment and will be made per case by the treating clinician, following standard of care.

Customary anesthesia and tooth preparation will be performed by the clinician as necessary for the particular indirect restoration. The gingival displacement procedure and impression will be made as described in this study protocol and as followed on the laminated clinical protocol sheet. If the clinician finds that the first impression is inadequate and chooses to make an additional impression, only the first impression will be evaluated for the study and a note will be indicated to record the number of impressions the clinician made to achieve an acceptable impression.

Patients will be given appropriate verbal and written post-procedure instructions; and appointments will be made for restoration try-in and delivery, as would happen as part of their regular treatment.

There are no potential direct benefits to the participant besides the fact that particularly close attention will be paid to the gingival displacement and impression procedures, and there will be close evaluation of impressions.

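### The primary discomfort score includes a rating taken before allocation, and possibly a second taken before the technique, with no baseline adjustment: precision is lost and the effect diluted, but neither arm is favoured.

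*Combined protocol and SAP*

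**What the plan says.** All references are to the combined protocol and SAP. Primary aim 3 (Specific Aims) is "the discomfort of the procedure as reported by the patient". Under Methods, the same discomfort question is put four times: "at the beginning of the treatment appointment, immediately before the impression procedure is initiated, immediately after the impression procedure is completed", and once more when the appointment ends. Each answer is scored 1 to 10. For the analysis, "The total score indicated by the sum of the 4 questions will be analyzed".

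On allocation, Methods states: "The treating clinician will open the allocation envelope after the tooth preparation is completed". Anaesthesia also comes before the technique: "Customary anesthesia and tooth preparation will be performed by the clinician".

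Under Statistical Analysis, the primary test for discomfort is an unadjusted Wilcoxon rank sum test. A Poisson model then adjusts for clinic, jaw and procedural materials, with the main interest in confidence intervals. Baseline discomfort is not among the covariates. The same section gives the range of the score as 0 to 40.

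**The concern.** A rating given before the patient's technique is known cannot respond to that technique. Adding it to the outcome leaves the expected difference between arms unchanged and raises the variance. The same rating would serve as a baseline covariate, but the plan does not use it as one.

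Discomfort is one of three primary outcomes, and the sample size was set on total errors only. Nothing in the plan shows that the discomfort comparison can spare this precision. A real difference confined to the later ratings might appear in the descriptive tables and still be missed by the primary test. The estimates would also understate the effect on discomfort of the procedure itself, which matters because the plan puts its main interest there on estimation.

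**Working it through.** **1. Which ratings can respond to the technique**

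- Rating 1 (start of appointment): precedes tooth preparation and the opening of the envelope. It cannot respond.
- Rating 2 (just before the impression procedure): open. Cord placement is step 2 under the heading "Traditional Corded Impression Procedure", which suggests that rating 2 comes first. But Methods also names displacement and impression as separate procedures, and step 2 speaks of removing the second cord before the impression is made. On that reading rating 2 follows cord packing. Methods says that the start and end of impression taking are defined earlier, but no listed step is marked as the start. Methods also says "The clinical instruction protocol is listed in Appendix A"; that appendix is not in the text available for this review.
- Ratings 3 and 4: follow the technique.

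**2. The plan's own power figure**

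The plan states 30 per group, 80% power, P = 0.709, two-sided 0.05, for total errors. Noether's formula gives N = (1.960 + 0.842)² / [3 × (0.709 − 0.5)²] = 7.85 / 0.131 = 59.9, or 30 per group, with 80.1% power. The figure reproduces. There is no counterpart for discomfort.

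**3. Standardised effect kept by the four-item sum**

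Assumptions: common correlation rho, and an equal effect on each responding rating. With unit SDs, Var(sum of 4) = 4 + 12rho, Var(2+3+4) = 3 + 6rho and Var(3+4) = 2 + 2rho.

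*Only rating 1 precedes the technique* (sum versus 2+3+4), share kept = sqrt[(3 + 6rho)/(4 + 12rho)]:
- rho 0.3: sqrt(4.8/7.6) = 0.79
- rho 0.7: sqrt(7.2/12.4) = 0.76
- rating 1 at half the SD, where Var(sum) = 3.25 + 9rho: 0.90 at rho 0.3, 0.87 at rho 0.7, and sqrt(3/3.25) = 0.96 at rho 0

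*Ratings 1 and 2 precede the technique* (sum versus 3+4), share kept = sqrt[(2 + 2rho)/(4 + 12rho)]:
- rho 0.3: sqrt(2.6/7.6) = 0.58
- rho 0.7: sqrt(3.4/12.4) = 0.52
- ratings 1-2 at half the SD, where Var(sum) = 2.5 + 6.5rho: 0.76 at rho 0.3 and 0.69 at rho 0.7

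**4. Dilution of the planned effect measures**

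Suppose the responding ratings alone give P = 0.709. Then d = sqrt(2) × z(0.709) = 0.778. At rho 0.5 with equal SDs:
- One early rating: d = 0.778 × 0.775 = 0.603, so P = 0.665. Power is 60% at 30 per arm and 82% at 50.
- Two early ratings: d = 0.778 × 0.548 = 0.426, so P = 0.618. Power is 36% and 54%.
- Undiluted: 80% and 95%.

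The Poisson ratio also moves toward 1, because the same early amount is added to both arms' means. In a simulation with assumed means 2, 3, 4 and 3, SD 2 and a 1-point effect on ratings 3 and 4, it was about 0.87 for the sum against 0.77 for ratings 3+4. In the same simulation the mean difference was unchanged (about −1.7 for both). With no effect, the sum rejected in 4.2-5.1% of runs.

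**5. Simulated power, 50 per arm, 1.2-point effect**

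Assumptions: ratings rounded and limited to 1-10; later ratings with mean 4 and SD 2; early ratings either the same or with mean 1.5 and SD 1; rho 0.3-0.7, plus settings in which rating 1 correlates only 0.1 with the rest. Sums are tested by Wilcoxon and adjusted outcomes by rank ANCOVA.

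| Ratings that respond | Planned sum | Alternative, adjusted for rating 1 |
|---|---|---|
| 3 and 4 | about 40-86% | 3+4: about 87-99% |
| 2, 3 and 4 | about 68-99% | 2+3+4: about 88-99% |
| 2 and 3 | 37-82% | 3+4: 33-61% |

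In the last row the sum beat ratings 3+4 in most settings. Ratings 2+3+4 adjusted for rating 1 matched or beat the sum in every setting, within simulation error.

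**The case against.** The strongest objection is that rating 2 may be asked with cords already in place. It would then be an outcome, perhaps the most relevant one. A reader might infer that two ratings certainly precede the technique and that the outcome should be ratings 3+4 regardless. The documents do not support that. Their wording points both ways, and the last row of the table shows that dropping a responsive rating 2 can cost more power than the planned sum loses. This part stands, and the remedy has to depend on the timing of rating 2.

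Second, randomisation balances the early ratings. That is correct. A reader might infer that the comparison is biased; it is not. The mean difference is unaffected and the type I error stays near nominal. What remains is lost precision, and effect measures closer to no effect than those for discomfort of the procedure alone.

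Third, rating 1 precedes anaesthesia and preparation, so it may correlate weakly with later ratings. This also stands. At a correlation of about 0.1, ratings 3+4 adjusted for rating 1 have about 87-95% power when both respond, and the adjustment itself adds essentially nothing. If in addition rating 1 is low and tightly grouped, and is the only early rating, removing it gains little (0.96 kept at zero correlation).

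Fourth, the study is exploratory. Discomfort is still a declared primary outcome, and the correction uses ratings already planned.

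**Conclusion.** The point holds for rating 1 without any assumption about timing: it precedes allocation, it is in the analysed sum, and no analysis adjusts for it. For rating 2 it holds only if that rating precedes the technique, which the documents leave open.

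The loss is one of efficiency and dilution, not of validity. Its size rests on assumed SDs, correlations and effects. It runs from negligible (only rating 1 early, low and weakly correlated) to large (two early ratings as variable as the later ones, where the sum keeps 0.52-0.58 of the standardised effect at rho 0.3-0.7). For non-negative correlation, the direction against the sum of the responding ratings does not depend on those values. This is a cheap improvement to a primary outcome, not a flaw that undermines the trial. The stated range of 0 to 40 is a minor slip, since 4 × 1 = 4 and 4 × 10 = 40; it does not affect the rank test.

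**What to change.** In a dated change made before any data by arm are seen:

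1. Take rating 1 out of the discomfort outcome and use it as a covariate, for example in a rank ANCOVA or a proportional-odds model.
2. State whether rating 2 is asked before or after any cord or surface optimizer is placed. If before, the outcome is ratings 3+4. If after, the outcome is ratings 2+3+4, and rating 2 must not be a covariate.
3. If a four-item total is still reported, give its range as 4 to 40.

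Rating 4 should also be shown separately. The clinician is told to "complete the impression for that tooth before proceeding to other teeth", so the end-of-appointment rating can reflect work on other teeth as well as repeat impressions.

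The cost is a few lines of wording. No new question is needed, provided that the four answers are stored separately. It is a small change to a primary outcome definition, so if made after data by arm are seen it should be labelled post hoc. The benefit of the adjustment itself may be slight if rating 1 correlates weakly with later ratings.

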- 2) Small diameter retraction cord, after it has been hydrated with Hemodent for 10 minutes, is tucked around the tooth in the space between it and its surrounding gum tissue. A second larger diameter retraction cord, also hydrated with Hemodent, will be placed over the first cord and tucked around the tooth. These cords will be left in place for a minimum of 8 minutes. These cords temporarily push the gum tissue back away from the tooth. (Before making the impression, the 2nd larger cord is removed, and the gums will stay back long enough for the impression material to seep around the tooth, thus allowing it to capture a copy of the entire tooth preparation.)
- 3) After a minimum of 8 minutes, the larger 2nd cord will be removed, and the tooth dried. Quickly, after confirmation of a dry field, the light body consistence impression material is syringed around the prepared tooth and across the occlusal surfaces of adjacent teeth.
- 4) An impression tray that has been filled with the heavy body consistency impression material is then placed over the arch of teeth, and gently pressed into place to ensure the teeth are completely covered with a uniform thickness of impression material. As the different impression material consistencies set, they fuse together into a single unit.
- 5) When removed from the mouth, the impression should contain a negative copy of both the prepared tooth and the teeth of that jaw.

Cordless Impression Procedure:

- 1) The prepared tooth is washed and dried, and assure hemostasis.
- 2) Apply B4 + surface optimizer.
- 3a) If 1 prepared tooth requiring an indirect restoration is being impressed, a single size (0.7mL) unit dose cartridge will be inserted into the digit power dispenser. If more than 1 prepared tooth requiring an indirect restoration is being impressed, a multi size (1.6mL) unit dose cartridge will be inserted into the digit power dispenser.
- 3b) Using the digit power dispenser, unit dose cartridge, and intrasulcular mixing tip, depress foot pedal and gently insert tip into the gingival sulcus of the prepared tooth, slightly apical to the preparation finish line. Material should flood the sulcus. Make sure to dispense material ahead of the intrasulcular tip, and completely around the prepared finish line, and then the tooth.

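### Impressions are kept only if an arm-specific instruction sheet was followed, a condition settled after randomization, and no analysis set is named

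*Combined protocol and SAP*

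**What the plan says.** The Methods paragraph on training says that instruction sheets for both techniques will be in the operatory and that "this protocol must be followed for the impression to be included in the study". It adds: "The clinical instruction protocol is listed in Appendix A".

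On timing, the randomization text in Methods says: "The treating clinician will open the allocation envelope after the tooth preparation is completed". Displacement and impression follow.

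The displacement steps are arm-specific. Under Traditional Corded Impression Procedure: "These cords will be left in place for a minimum of 8 minutes", and then "Quickly, after confirmation of a dry field" the light-body material is syringed. Under Cordless Impression Procedure: "Apply B4 + surface optimizer", then dispensing through an intrasulcular tip.

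Three other statements in Methods bear on who is analysed. On eligibility: "The patient will be dropped from the study if inclusion/exclusion criteria are not met". On repeat impressions: "only the first impression will be evaluated for the study". On scoring, two examiners evaluate every impression.

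The Statistical Analysis section gives the outcomes, the Wilcoxon rank-sum test and an adjusted Poisson regression by impression group. It names no analysis population. The form for the treating clinician lists only eligibility reasons for dropping a patient and has no field for a departure from the sheet.

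**The concern.** Randomization protects the comparison only while membership of the analysed groups does not depend on what happens afterwards. Here it may. Whether the sheet was followed is decided after allocation, during an unblinded procedure, against different requirements in each arm.

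A link with the outcome is plausible from the documents. Several steps sit close to errors scored in Appendix B: cord removal to attached retraction cord, hemostasis and a dry field to blood on the impression, dispensing around the finish line to voids and lack of wash material. Attached cord is naturally a corded-arm error, so the link could differ by arm, and then even equal exclusion rates can bias the result.

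The number of errors is a primary outcome. The study is exploratory and its adjusted analysis stresses estimation with confidence intervals, so a shifted estimate and poor interval coverage matter as much as false positives. Time and discomfort are affected only if those data are dropped along with the impression, which the text does not say.

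**Working it through.** **The plan's own figure.** Statistical Analysis states 30 per group, 80% power, probability 0.709, two-sided 0.05. By Noether's formula, total N = (1.960 + 0.842)² / (12 × 0.25 × (0.709 − 0.5)²) = 7.849 / 0.1310 = 59.9, or 30 per group. The figure reproduces. Methods plans 100 participants in balanced blocks of 4, so 50 per arm is used below.

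**Does any other text neutralise the condition?**
- The first-impression rule keeps an inadequate first impression. It does not bring back one left out because the sheet was not followed.
- Scoring of all impressions either means all included impressions or conflicts with the condition.
- The eligibility drop rule does not cover departures.
- No analysis set is stated, so this is an unspecified set plus an exclusion rule, not a declared per-protocol analysis.

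**Size, under assumptions.** The documents give no departure rate and no relation to errors, so both are varied. No true difference; 50 per arm; errors Poisson with mean 2, capped at 13; a latent departure score with correlation ρ to the latent outcome; cases above the exclusion percentile removed; tie-corrected Wilcoxon test at two-sided 0.05; 6000 simulated trials per cell. Positive bias means that the arm losing more cases looks better. Entries are bias in errors / type I error.

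| Excluded | ρ = −0.3 | 0 | 0.3 | 0.5 | 0.7 |
|---|---|---|---|---|---|
| 5% v 0% | −0.05 / 5.6% | 0.00 / 4.6% | 0.04 / 5.1% | 0.08 / 5.6% | 0.12 / 5.8% |
| 10% v 0% | −0.08 / 5.7% | 0.00 / 4.7% | 0.08 / 5.6% | 0.14 / 7.0% | 0.21 / 9.2% |
| 20% v 5% | −0.10 / 6.1% | 0.00 / 5.3% | 0.10 / 6.3% | 0.17 / 8.6% | 0.24 / 12.6% |
| 30% v 5% | −0.15 / 8.2% | 0.00 / 5.2% | 0.16 / 7.6% | 0.27 / 13.9% | 0.38 / 23.4% |

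A second set of 4000 trials per cell gave type I errors at ρ = 0.7 of 6.6%, 12.1% and 24.9% for 5% v 0%, 20% v 5% and 30% v 5%; pooled over both sets, 6.1%, 12.4% and 24.0%. It also gave the mean ratio of errors (truth 1) and the coverage of an unadjusted nominal 95% Poisson interval:

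| Excluded | ρ = −0.3 | 0 | 0.3 | 0.7 |
|---|---|---|---|---|
| 5% v 0% | 1.02 / 94.9% | 1.00 / 95.0% | 0.98 / 95.0% | 0.94 / 92.9% |
| 20% v 5% | 1.05 / 94.5% | 1.00 / 95.1% | 0.95 / 93.9% | 0.87 / 89.1% |
| 30% v 5% | 1.08 / 92.5% | 1.00 / 94.9% | 0.92 / 92.7% | 0.79 / 76.6% |

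**Equal exclusion rates.** With the same ρ in both arms (10% v 10%, 20% v 20%), bias is within 0.01 errors and type I error 4.3% to 5.3%. With ρ of 0.3 to 0.7 in one arm and 0 in the other, 10% v 10% gives 0.09 to 0.20 errors and 5.9% to 8.8%.

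**Analysing the same data as randomized.** Bias within 0.01 errors and type I error 4.4% to 5.5% in every cell.

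**Power cost of keeping everyone.** Suppose a share f of cordless cases is non-adherent and gets no effect at all. The design probability becomes 0.709(1 − f) + 0.5f: 0.699, 0.688 and 0.667 at f = 5%, 10% and 20%. Under a normal shift of 0.778 SD (equivalent to 0.709), simulated power at 50 per arm is 96.3% at f = 0, then 94.4%, 91.6% and 84.2%.

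**The case against.** The sentence sits in a paragraph on training, and nobody is assigned to judge adherence. It could be read as a conduct standard that was never meant to exclude patients. That reading is possible, but the words make inclusion conditional and no analysis set contradicts them, so clarification is needed either way.

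The largest figures need frequent, uneven and outcome-related departures together. Nothing in the documents suggests rates as high as 30%, and training, calibration and the sheet in the operatory point to fewer. This stands, and it limits the size of the point. The coverage figures are also unadjusted, whereas the plan adjusts for covariates.

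The power calculation and the Budget correspond to 30 per arm, not 50. At 30 per arm, type I error for ρ of 0.3 to 0.7 is lower: 5.1% to 5.6% (5% v 0%), 6.1% to 9.1% (20% v 5%) and 6.6% to 15.8% (30% v 5%), with bias unchanged. Dilution costs more: separate simulations put power at 82% to 84% with full adherence, then about 78%, 71% to 73% and 62% to 63% at 5%, 10% and 20% non-adherence. This stands, but it changes the size and not the substance. The stated enrolment is 100.

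Washing and drying, tray seating and removal are common to both arms; only displacement and syringing differ. That is correct, and those are the steps at issue.

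No part of the available text is labelled Appendix A. The procedural steps in Methods are taken as the sheet's content because Methods ties the two together. If Appendix A defines a departure, or says how one is noted, the corresponding sub-point falls. The exclusion condition remains.

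**Conclusion.** The concern holds. The plan contains a post-randomization inclusion condition that differs by arm, and no analysis set that limits it. Its size and direction cannot be known from the documents; all exclusion rates, correlations and the mean of 2 errors are assumptions. The effect is negligible if departures are rare or unrelated to errors. It is material if they are frequent, related to errors, and uneven in rate or in that relation. If departures go with fewer errors, the bias reverses. The change should be made because it closes the bias path cheaply. Confidence in the practical size is moderate at best.

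**What to change.** Replace the condition in the training paragraph with an analysis-set statement, repeated in Statistical Analysis:

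*The primary analysis includes every eligible randomized patient in the allocated arm, using the first impression made, its recorded time and the discomfort scores, whether or not the instruction sheet was followed.*

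Also:
- State that all eligibility criteria are confirmed and recorded before the envelope is opened. Finish-line depth is known only after preparation, so without this an eligibility drop could depend on the arm.
- Define a departure from the sheet, unless Appendix A already does.
- Add a departure field (yes/no, with reason) to the clinician form.
- Report departures, and eligible randomized patients with no score, by arm and reason.
- Keep the protocol-followed subset as a sensitivity analysis.

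The cost is two sentences, one definition, one form field with its reason, and a short additional table and analysis. No clinical procedure changes. The statistical price is dilution by non-adherent cases. At 50 per arm, power for the design effect stays above 80% even at 20% non-adherence. At 30 per arm it would drop below 80% from about 5% non-adherence.
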